### Settings and Targeted Population

Ambulatory dementia patients will wear the localization device in these studies. However, the study participants actually providing data in these studies will be paid and unpaid caregivers. Study 2a will be conducted in the memory and skilled care units at Oak Hammock Senior Living Center in Gainesville, FL. Five ambulatory patients with moderate dementia (Mini-mental State Exam (MMSE) scores of 10-18) in each setting (memory/skilled) will be identified and with consent of their legal proxies included in

their study. Participants in Study 2a will include 10 persons with moderate dementia and their six paid caregivers at Oak Hammock Senior Living Center. These professional caregivers preside over multiple patients at one time, so only six paid caregivers are needed for these 10 patients. Separate day and evening shift assigned primary caregivers (typically certified nursing assistants) will be provided the smartphone tool used for monitoring location. Study 2b will be conducted with community dwelling dementia patients with mild dementia (MMSE 19-25). Participants in Study 2b will include 80 community dwelling persons with mild dementia and their 80 unpaid, family caregivers who all reside in the Gainesville, Florida area. Caregivers for these patients will have at least 3-times weekly contact with the patients. Cohabitation will not be required but will be recorded will caregiver relationship (spouse, adult child, other family, friend) as covariates. Presumed etiology of the dementia will be recorded but will not be a selection factor (Alzheimer's, vascular dementia, Lewy body dementia).

### Study 2a

#### Persons With Dementia

##### *Inclusion Criteria*

- Resides in memory care or skilled nursing at Oak Hammock Senior Living Center
- Moderate dementia (MMSE of 10-18)
- Ambulatory (without or with cane, walker or wheelchair assist)
- A legal proxy that can provide consent

### Study 2b

#### Persons With Dementia

##### *Inclusion Criteria*

- Resides in independent living setting in community.
- Mild dementia (MMSE of 19-25)
- Ambulatory (without or with cane, walker or wheelchair assist).
- Has a legal proxy that can provide consent.

### Care Partners

##### *Inclusion Criteria*

- Speaks English
- Be 21 years of age or over
- Has at least three times per week direct contact with person with dementia (PWD)
- Consents to participate in the study

##### *Exclusion Criteria*

- Is not fluent in written or spoken English
- Indicate an unwillingness to use the *Activlink*
- History of Major Mental Illness for patient or caregiver

### Vulnerable Population

Pregnant women, decisionally impaired individuals, and UF/OneFlorida Institution Students may be vulnerable populations that may be included in this study but not purposely targeted. In fact, it is unlikely that our subjects will be pregnant because of the age the majority of our participants will be. Pregnant woman are not excluded from the study but are unlikely to be participants as those females of childbearing age generally fall outside the range of the typical family member of a person with dementia (PWD). However, it is important to include pregnant women in this project because we would be losing family members of PWD if we exclude women under the age of 62. Nonetheless, the study will use no drugs or devices that are potentially harmful to the fetus. These individuals will be fully disclosed and will understand they can refrain from participating in the study at any time. They will also be told that no drugs or devices are used in the study that could be harmful to the fetus.

As for decisionally impaired individuals, the primary goal of this study is to provide a practical solution of monitoring the location of individuals with dementia to reduce caregiver stress and burden and improve quality of life. Early stage dementia symptoms include forgetfulness, patients unable to recall familiar people's names or recent events. These individuals can often function independently or with minor assistance from others. Monitoring location in these individuals who continue to reside in community could be extremely advantageous to the individual themselves and to their possible caregiver to avoid them getting lost in unfamiliar environments and also to assure they are following routines. In the moderate stages of dementia, marked increases occur in disorientation, memory loss, and confusion exaggerating the need for monitoring. We believe these individuals, along with their caregivers, would significantly benefit in location monitoring as problems with disorientation become more prevalent. All individuals with dementia must have a legal proxy that can provide consent to support the patients assent. Both patients with dementia and their caregivers will be informed that their participation in the study is entirely voluntary, and though no harm is expected from their participation, they can stop participating at any point of the study. Furthermore, both patients and caregivers will be told that their choice of whether or not to participate will not affect their clinical care.

It is important that we include UF/Shands/VA/OneFlorida Institution Staff in the study because these individuals could potentially be caregivers of people with dementia. These individuals will be fully disclosed and will understand they can refrain from participating in the study at any time. They will also be told that no drugs or devices are used in the study that could elicit harm. They will also be told that their participation in the study will remain confidential and not affect their position as UF/Shands/VA/OneFlorida staff.

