While progression of each patient's dementia varies, one of the most common and burdensome similarities in behavior is wandering, or *dementia elopement* [14],[25]. It is estimated that 60% of AD patients exhibit this behavior and are at risk of disorientation and associated injuries [26],[27]. Studies show that half of all wanderers lost for 24 hours or more will be injured or die [28],[29]. The advancement of AD tends to increase the disorientation in time and space, increasing the probability of elopement behavior [2],[30],[31]. A system providing caregivers the ability to localize a wandering patient would reduce the emotional burdens of caregiving and enhance the safety of dementia patients. This localization tool, which automates the monitoring process and provides rapid alerts when a patient's movement indicates undesired wandering, holds significant potential. The tool would renew caregiver's abilities to function in normal daily activities and increase economic freedom from the great cost associated with caring for a patient or loved one suffering from dementia.

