### Data Safety Monitoring Board

As the proposed project will pose minimal risks to study participants the Principal Investigator (PI), [name], will serve as the primary monitoring entity of this study. The proposed study involves no invasive procedures and there will be no physical risks to study participants. The consideration of need is potentially stressful, and thus there are possible psychological risks for the caregiver a relative with dementia. However, potential participants with a history of serious mental illness (i.e., any major psychiatric disorder) will not be included in the study and since the research team has considerable experience providing psychosocial support to dementia caregivers on various research protocols, serious psychological risks are unlikely to occur. The potential social or legal risks for the participants relate only to possible violations of confidentiality. Additional monitoring support will be provided by the Independent Study Monitor (ISM), [name].

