## **7. Possible Discomforts and Risks:**

This study focuses on the utility of a technology that tracks the location of a person with dementia. The first primary risk is a loss of privacy for the person with dementia. The technology will track throughout the environment, so it will be possible to infer when he or she uses the bathroom, goes to bed, etc. The second primary risk could be a false sense of security for the caregiver about the whereabouts of the patient. For example if the insole is not operating correctly or is not worn, the caregiver may believe the person with dementia is in a safe location when they are not.

Participation in this study is considered to be of minimal risk compared to the standard unmonitored living arrangement of the persons with dementia and their caregivers. Nevertheless, we will engage in thorough safety monitoring. Furthermore, [name] has considerable experience working with older adults and is equipped to handle all emergencies. Given our extensive research on dementia caregiving populations as well as the general literature, it is unlikely care partners or persons with dementia will be under the age of 30; therefore, we do not anticipate requiring additional consent mechanisms or protections of risk for individuals under the age of 21. All interviews will be conducted by either [name] or a research assistant. These interviews will be in-person. Staff and procedures for handling medical emergencies are in place at Oak Hammock. Medical emergencies occurring for community dwelling residents will be addressed using the standard 911 system.

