## **8. Possible Benefits:**

We believe that participation in the Activlink evaluation will yield benefits for participants. The expected benefits for participants are the feeling one might experience knowing they are helping to advance an aid that may potentially reduce the burden of caregivers. Utilization of the Activlink insole and mobile application will provide caregivers of PWD with greater opportunities to continue with their daily activities with reduced concern that they must directly and continuously view their PWD, as the new device can assist them by notifying the caregiver where the PWD is located at any given moment.

This aiding and supporting the advancement of new technology to further support caregiver operation is sufficient for the subjects to understand the risks associated with this study.

Studies that evaluate the efficacy of assistive technologies to enhance living with dementia are underdeveloped. The proposed project aims to fill this scientific and clinical gap by evaluating a novel, insole sensor system with its associated mobile application that will allow caregivers of PWD to more fully engage in necessary activities other than constant monitoring. We anticipate that Activlink will offer robust support for care partners, professional staff, and families of PWD in various communities.

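### What caregivers are told about device harm, and the no-physical-risk statement, contradict the false-security risk that the protocol's own section 7 calls primary

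*Combined protocol and SAP*

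**What the plan says.** Four parts of the combined protocol and SAP bear on this.

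- **Section 6, Vulnerable Population.** Institution staff (UF/Shands/VA/OneFlorida) may be caregivers of people with dementia and may take part. Of them it says: "They will also be told that no drugs or devices are used in the study that could elicit harm". A milder message goes to all patients and caregivers: "though no harm is expected from their participation, they can stop participating at any point of the study".
- **Section 6, Data Safety Monitoring Board.** "The proposed study involves no invasive procedures and there will be no physical risks to study participants". The section then discusses psychological risk to the caregiver and confidentiality. It makes the Principal Investigator the primary monitor because the project is of minimal risk, with support from an Independent Study Monitor. False security is not mentioned.
- **Section 7, Possible Discomforts and Risks.** The first primary risk is loss of privacy. Then: "The second primary risk could be a false sense of security for the caregiver about the whereabouts of the patient". The example given is an insole that malfunctions or is left off, so that the patient is wrongly thought to be safe. The section goes on to rate participation as minimal risk relative to unmonitored living, and it promises thorough safety monitoring.
- **Section 4, Background.** On patients who wander, it reports that "half of all wanderers lost for 24 hours or more will be injured or die".

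**The concern.** One section has a group of caregivers told that the device cannot cause harm. Another says that participants face no physical risk. A third names a way in which the device can leave a patient unsupervised and in danger. The purpose of the system is to let caregivers reduce direct oversight, so a caregiver's understanding of when the display can be trusted bears on patient safety.

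Followed as written, the plan gives some participants an assurance that its own risk section denies. The monitoring rationale also declares the risk minimal without mentioning one of the two risks that section 7 puts first.

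**Working it through.** The plan states no figure on this point, so the check is mainly a comparison of texts.

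**Step 1. Scope of the assurance to staff.** The sentence could be meant as harm to the staff member only. The parallel sentence for pregnant participants, in the same section, is expressly limited to harm to the fetus. The staff sentence has no limit. A caregiver hearing it would reasonably take it to cover the person they care for.

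**Step 2. Is false security a route to physical harm?** Section 7 describes a patient believed safe who is not. Section 4 links being lost for 24 hours or more with injury or death. The section 4 figure is conditional on that duration and is not a rate for this trial, but it shows that the harm in question is physical. The absolute statement of no physical risk therefore conflicts with the protocol's own account.

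**Step 3. Does the plan treat the display as infallible?** It does not. Measures and Devices Proposed sets a one-week location check in Study 2a, and the efficacy study is delayed only if accuracy falls below 95%.

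- Planned data points: 10 patients × 2 per day × 7 days = 140, which matches the stated 140.
- 7 wrong of 140: 133/140 = 95.0%, no delay.
- 8 wrong of 140: 132/140 = 94.3%, delay.
- With 7 wrong of 140, the exact (Clopper-Pearson) 95% interval for the error rate is 2.0% to 10.0%. This treats the 140 points as independent, although they come from only 10 patients.

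This shows only that the plan accepts some wrong locations. It does not measure harm: a wrong location is not the same as an unsafe patient, and 95% is a threshold for delay, not an expected accuracy.

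**Step 4. Who is affected?**

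- Absolute assurance: staff caregivers only; number not given.
- Milder message that no harm is expected: all planned participants, 10 + 6 in Study 2a and 80 + 80 in Study 2b, 176 in total. This is an expectation and not a denial of risk, so the conflict is weaker.
- Caregivers who would need to know the device's limits: 6 + 80 = 86.

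**Step 5. The stated basis for monitoring.** The Data Safety Monitoring Board section rests its arrangement on minimal risk. Section 7 gives the same rating, after naming false security and relative to unmonitored living. The two sections agree on the rating. They differ on which risks it was weighed against.

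**The case against.** The best defence is that this is loose wording. The staff sentence sits in a passage about protecting employees as a vulnerable group, where harm to the employee is a natural reading, and the text says these people will receive full disclosure. The consent pages are not available, so they may already explain the device's limits. Study 2a caregivers are asked to mark displayed locations as correct or incorrect, which itself shows them that the display can be wrong. This defence has some force: what caregivers would actually be told cannot be fully checked. It does not remove the conflict, because the protocol instructs that an unlimited assurance be given, and a fuller consent form would then contradict that instruction.

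A reader might also infer more than the documents support.

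- *That the monitoring level rests on a false statement.* Its stated basis is minimal risk, and section 7 keeps that rating after naming false security. The assurance to staff plays no part in it.
- *That nobody is assigned this risk.* The investigator monitors the study as a whole, the Independent Study Monitor's role is not confined to particular risks, and section 7 promises safety monitoring and gives emergency arrangements for both settings.
- *That the sentence "The potential social or legal risks for the participants relate only to possible violations of confidentiality" is also contradicted.* It concerns social and legal risk, and false security is neither.
- *That section 8 guarantees accuracy.* It says the device can assist by "notifying the caregiver where the PWD is located at any given moment". That describes a benefit and makes no claim about error.
- *That wrong displays can be counted per day.* Any such count needs an assumed number of checks and treats the 95% threshold as the true accuracy.

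**Conclusion.** The contradiction is real and should be corrected before caregivers are briefed. The unlimited assurance to staff caregivers and the statement of no physical risk cannot stand beside the second primary risk in section 7. The monitoring section's minimal-risk rationale is incomplete because it never states that risk.

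The consequence lies in participant information and patient safety; no endpoint, comparison or sample size changes. Its size cannot be put as a number from the documents.

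The conclusion rests on two readings: that the staff sentence means what it says without an implied limit, and that a patient wrongly believed safe can come to physical harm, as section 4 implies. It does not extend to the monitoring level being wrong, the risk being unassigned, or any particular rate of wrong displays. The risk is called device-related and not device-caused, because section 7 includes the insole not being worn.

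**What to change.** Reconcile the three sections, with section 7 as the reference for what the risks are:

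1. In Vulnerable Population, delete or correct the sentence telling staff caregivers that no device could cause harm, and check that the milder message to all participants is given together with the section 7 risks.
2. In Data Safety Monitoring Board, replace the statement of no physical risk with the false-security risk, so that the minimal-risk rationale is argued against it.
3. Have every caregiver told, on receiving the device, that the displayed location can be wrong and carries no information when the insole is not worn.
4. Name this risk among those that the investigator and the existing Independent Study Monitor already oversee.

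The cost is a few sentences in the protocol and in what caregivers are told. Better-informed caregivers may use the device somewhat more cautiously, which could reduce any saving in caregiving time; the documents give no basis for saying by how much. Independent review of every relied-on wrong location is not proposed: it would need new incident recording across 90 patients (10 + 80), and location verification is described only for the Study 2a pre-trial week.

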#### *Measures and Devices Proposed*

Dementia patients will wear the provided insole inserted into their own shoes. The insole will have a small electronic sensor that measures acceleration, foot force, and/or orientation. The subject will then walk for a series of trials to determine the wearability while in motion. Data will be transmitted securely from the sensor system to the data collection device, a laptop or desktop computer. Once collected, the data file will be securely stored. Caregivers will complete paper records of caregiver activity, burden, and quality of life.

**Location Validation** Measures in Study A. For one-week prior to the formal efficacy trial, the technology will be deployed to all 10 participants. Once per shift at a randomly generated time, the paid caregivers a notification (a buzz on the smartphone) and asked to respond 1) location visually verified to be correct 2) location visually verified as incorrect or 3) unable to provide verification at that time due to other responsibilities. In the case of the last response, the system will auto generate another notification latter in that shift. Caregivers will be asked to verify location as either correct or incorrect at least one time per shift. Ten patients tracked at least twice per day over 7 days will provide 140 data points to assess the accuracy of the system at tracking patient location. An accuracy of less than 95% will result in our delaying the efficacy study until technical improvements can improve the accuracy of the deployed system.

**Primary Efficacy Outcome.** Primary outcome measure in both studies will be the Caregiver Activity Survey (Davis, et al., 1997). This well validated scale requires caregivers to report on amount of time spent caregiving for a particular patient. It has high test-retest reliability (.88) and documents an increase in time spent in supervision as MMSE declines overtime (Marin et al., 2000). Caregivers will be asked to complete this instrument once every two weeks.

**Secondary Efficacy Outcomes** in Study b. Caregivers in study b will also complete the short-form of the Zarit Caregiver Burden scale [32] and the AD Quality of Life Scale [33]. Both scales are reliable, well validated, and the most widely used measures of careburden and AD-QoL.

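### The 95% location gate is scored by the caregiver's own, apparently unblinded, correct/incorrect call with no definition of correct, so the go/no-go result may not reflect true accuracy

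*Combined protocol and SAP*

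**What the plan says.** The location validation is described in section 6 of the protocol, under Measures and Devices Proposed. For one week before the efficacy trial, "the technology will be deployed to all 10 participants". Once per shift, at a random time, the paid caregiver's smartphone buzzes and the caregiver picks one of three answers. Two are scorable: "location visually verified to be correct 2) location visually verified as incorrect". The third, "unable to provide verification at that time due to other responsibilities", is not scored and triggers another notification later in the shift.

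The yield is stated as "Ten patients tracked at least twice per day over 7 days will provide 140 data points", and the decision rule as "An accuracy of less than 95% will result in our delaying the efficacy study".

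Under Settings and Targeted Population, the day and evening caregivers "will be provided the smartphone tool used for monitoring location", and "only six paid caregivers are needed for these 10 patients".

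Neither the protocol nor the Statistical Analysis Plan says what counts as a correct location (room, zone, distance or time window). Neither has the caregiver record where the patient was, provides a second observer, or says that the system's location is hidden during a check. The Statistical Analysis Plan does not mention the validation week.

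**The concern.** The gate is meant to measure how often the system puts the patient where the patient actually is. That needs two separate readings, one from the system and one from an observer, and a rule for comparing them. The plan collects only the observer's verdict on the comparison.

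Two weaknesses follow. First, a caregiver can call a location correct or incorrect only by knowing what the system reported, and the same person carries the phone that reports it. A rater who knows the answer under test may give it the benefit of the doubt when the patient is in a doorway or the next room. Second, with no tolerance set, each of the six caregivers decides alone where a near miss ends. Some may be lenient. Others may be strict, or may mark a location incorrect because the patient moved between the buzz and the sighting.

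At stake is a go/no-go decision. Section 7 (Possible Discomforts and Risks) names a caregiver's false sense of security about the patient's whereabouts as one of two primary risks. A system that passes when it should not carries that risk into the trial, and a null efficacy result would then be harder to interpret. A good system that fails delays the trial for no reason.

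**Working it through.** **The plan's own figure.** 10 patients × 2 checks per day × 7 days = 140, which matches the protocol. The pass mark is 0.95 × 140 = 133, since 133/140 = 95.0% passes and 132/140 = 94.3% does not.

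**Inputs not in the documents.** These are the true accuracy p, the share k of wrong locations that the caregiver accepts, and the share r of correct locations that the caregiver rejects. All three are assumed, so ranges are shown.

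**Formula.** The expected recorded accuracy is q = p(1 − r) + (1 − p)k. The chance of passing is P(X ≥ 133) for X binomial with n = 140 and probability q, treating checks as independent.

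**Wrong locations accepted (r = 0).**

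| True p | k | q | Chance of passing |
|---|---|---|---|
| 0.90 | 0 | 0.900 | 2.6% |
| 0.90 | 0.10 | 0.910 | 5.8% |
| 0.90 | 0.25 | 0.925 | 16.8% |
| 0.90 | 0.50 | 0.950 | 59.9% |
| 0.90 | 0.75 | 0.975 | 97.5% |
| 0.93 | 0 | 0.930 | 22.9% |
| 0.93 | 0.25 | 0.9475 | 54.5% |

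The share that lifts the expected recorded figure to exactly 95% is k = (0.95 − p)/(1 − p). This is 0.05/0.10 = 50% at p = 0.90 and 0.02/0.07 = 29% at p = 0.93.

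**Correct locations rejected (k = 0).** At p = 0.97 and r = 0.05, q = 0.97 × 0.95 = 0.9215 and the chance of passing is 13.3%. With no error (r = 0) it is 93.9%.

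**Both errors together.** At p = 0.90, k = 0.50 and r = 0.05, q = 0.855 + 0.050 = 0.905 and the chance of passing is 3.9%. The two errors can largely cancel, so the net direction is not known in advance.

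**Unscored answers.** Suppose a share g of wrong locations draws the unable answer and is replaced by a later check. Then q = p/[p + (1 − p)(1 − g)]. At p = 0.90 and g = 0.50, q = 0.90/0.95 = 0.947 and the chance of passing is about 54%.

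**Sampling error alone (k = r = g = 0).** The chance of passing is 39.3% at p = 0.94, 22.9% at 0.93, 12.0% at 0.92 and 2.6% at 0.90. Allowing for 14 checks clustered within each patient (beta-binomial, assumed intraclass correlation 0.05 to 0.20) raises the 2.6% to between 6.4% and 16.9%.

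**The case against.** The strongest reply is that the caregiver physically sights the patient. A reader might infer that the reference standard is derived from the device, but the documents do not support that. It is a human observation, and when the patient is plainly elsewhere the phone's display should sway nobody. This stands. The weakness is that the rating appears unblinded and the observation is not recorded separately, and it bears mainly on near misses.

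The order of events is also not written down. The protocol does not say that the caregiver sees the app's location before looking for the patient. That is inferred from the answer options and from the caregivers holding the phone.

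A reader might further infer that the recorded percentage must be too favourable. That does not follow: an undefined criterion can also produce rejections, and nothing in the documents fixes k, r or g. At k = 0.25 the gate still stops a true 90% system about 83% of the time (100 − 16.8). If a next-room reading is good enough for finding a patient, accepting it may not be an error at all, but the plan would have to say so.

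Finally, this is a readiness check. It does not enter the primary outcome, the Caregiver Activity Survey, and no bias in the efficacy comparison follows from it. Section 6 also refers to a Phase I technical evaluation of the prototype, so this is not necessarily the only accuracy evidence that exists, although it is the only accuracy check this protocol sets out for the deployed system.

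**Conclusion.** The point holds as a weakness in how the gate is measured. The 95% has no stated unit of correctness, and it rests on an apparently unblinded verdict with no separate record of where the patient was. The result may therefore differ from true accuracy. Unblinded confirmation may push it towards the device on near misses, and the missing definition can push it either way.

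The size depends on assumed error shares. A true 90% system's chance of passing moves from 2.6% to 17% or 60% as k goes from 0 to 0.25 or 0.50. A true 97% system's chance falls from 94% to 13% if 5% of correct locations are rejected. The absence of a definition depends on none of these assumptions; the lack of blinding is an inference.

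A reader might also conclude that a blinded reference would keep every system below 95% out. It would not: a point-estimate rule on 140 checks passes a true 94% system 39% of the time with a perfect reference. That is a separate limitation.

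**What to change.** At each random notification, hide the app's location until the caregiver has sighted the patient and tapped the room or zone from a fixed list for the unit. Have software compare that entry with the system's estimate time-stamped at the moment of entry. Before the week starts, define correct as the same listed room or zone, and fix the list then, because zone size determines how hard 95% is to reach. Compute the 95% from the software comparison.

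Keep the random timing, the 140 checks, the 95% threshold and the unable option. With the location hidden, the choice of that option can no longer depend on whether the displayed location looks wrong.

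The cost is a small app change, a room list for two units (memory and skilled care), a short addition to the protocol, and slightly longer checks because the caregiver is not told where to look. No extra staff are needed. The change does not reduce sampling error in the gate.
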